32. Transnational Research.....	19
33. Drugs or Devices	19
Checklist Section	20

PROTOCOL TITLE: “Evaluating the efficacy of micro-fragmented adipose tissue and intra-articular corticosteroid injections for symptomatic knee osteoarthritis: a randomized, placebo controlled study”

1. Objectives

- 1.1. *The purpose of this study is to evaluate the possible benefits of reduced joint pain and increased joint functionality in participants with knee osteoarthritis after the injection of Lipogems®. Based on limitations of prior research, intra-articular corticosteroids are included as a study group to be evaluated for impact on pain relief and joint functionality in comparison to placebo.*
- 1.2. *We hypothesize that participants who receive an injection of Lipogems® will experience a decrease in pain of the affected knee and an increase in joint functionality in comparison to placebo. We also hypothesize that participants who receive an intra-articular corticosteroid will experience decreased pain or improved functionality in the affected joint.*

2. Background

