(over time) and between-patient variations, and are more flexible in making inference on group differences. The method also allows for the inclusion of multiple covariates (see below) in the model to quantify effects attributable to the treatments. We will also consider repeated measurement analysis of covariance and pairwise comparison (e.g. t-tests) to validate our analysis with respect to robustness and sensitivity. We will follow LaPrade’s recent recommendations of minimal reporting requirements for treatments that potentially include mesenchymal stem cells, such as Lipogems®. This includes age, gender, diabetes status, inflammatory conditions, pre-existing joint problems, and current NSAID use.¹⁹ Since patient perception of post-treatment pain as measured by the VAS scale is a main variable of interest in our hypothesis, we searched the literature for previous studies in which the variability of pain using a VAS scale was investigated.²⁰⁻²³ We estimated that the standard deviation likely to be found for our own observations will be approximately 35 on a 100 point scale, conservatively. We assume that most clinicians will consider a difference in post-treatment pain of about 15 points to be clinically important, as supported by Tashjian *et al*, who estimated 1.4 cm as the minimal clinically important difference on a 10 cm scale. To determine an adequate sample size for our pilot, we assumed average change in pain score over the follow-up to be 10-15, and standard deviation to be 10-20. To have 80% power with a 5% Type I error rate, an approximate 2-way ANOVA model suggest sample size in the range of 18-49 per group. We adopt $n=22$ as our minimum sample size per group based on the assumption of 15-point change in pain score over time on average and a 20-point standard deviation over time. Within the recruitment time window, we will aim to enroll $n=25$ or more participants in each of the three treatment arms so long as the logistics permit. We expected the mixed-effect model will increase the power by utilizing the longitudinality of the data, compensating potential loss of power due to drop-outs and serial correlation.

6. Study Timelines

6.1. Describe:

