7. Upon completion of their 1-year questionnaires, participants who were randomized to receive placebo injections will be offered the choice to cross-over to the corticosteroid group. Whether they choose to have the injection or not, their participation in the study will be completed.

PROTOCOL TITLE: “Evaluating the efficacy of micro-fragmented adipose tissue and intra-articular corticosteroid injections for symptomatic knee osteoarthritis: a randomized, placebo controlled study”

13. Data Analysis

- 13.1. *We will take advantage of the 5-repeated measurements of joint pain and functionality from each patient, and compare the post-treatment trajectory of joint pain and functionality over follow-up between a pair of treatment groups. This approach facilitates group comparisons (1) at individual follow-up times, (2) life course of effects over the entire follow-up period. This will be done by means of mixed-effects regression models which incorporate both within-patient (over time) and between-patient variations, and are more flexible in making inference on group differences. The method also allow for the inclusion of multiple covariates (see below) in the model to quantify effects attributable to the treatments. We will also consider repeated measurement analysis of covariance and pairwise comparison (e.g. t-tests) to validate our analysis with respect to robustness and sensitivity.*

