- 13.2. *Since patient perception of post-treatment pain as measured by the VAS scale is a main variable of interest in our hypothesis, we searched the literature for previous studies in which the variability of pain using a VAS scale was investigated.²⁰⁻²³ We estimated that the standard deviation likely to be found for our own observations will be approximately 35 on a 100 point scale, conservatively. We assume that most clinicians will consider a difference in post-treatment pain of about 15 points to be clinically important, as supported by Tashjian et al, who estimated 1.4 cm as the minimal clinically important difference on a 10 cm scale. To determine an adequate sample size for our pilot, we assumed average change in pain score over the follow-up to be 10-15, and standard deviation to be 10-20. To have 80% power with a 5% Type I error an approximate 2-way ANOVA model suggest sample size in the range of 18-49 per group. We adopt n=22 as our minimum sample size per group based on the assumption of 15-point change in pain score over time on average and a 20-point standard deviation over time.*

14. Provisions to Monitor the Data to Ensure the Safety of Subjects

- 14.1. *Corticosteroids are standard of care. Lipogems® is approved for use in orthopaedics and arthroscopic procedures. Participants will be closely followed by the participating clinicians/investigators through the follow-up visits required for participation. All measures will be taken to ensure that participants receive appropriate care.*
- 14.2. *Patients will be informed of the risks of participating prior to enrolling in the study and may choose to enroll or not enroll. They will be reminded of expected post-procedural findings and will be monitored for adverse reactions by the participating clinicians at their follow-up visits.*
- 14.3. *The data monitoring committee will consist of [name], [name] [Orthopaedic Sports Medicine], [name] [Orthopaedic*

PROTOCOL TITLE: “Evaluating the efficacy of micro-fragmented adipose tissue and intra-articular corticosteroid injections for symptomatic knee osteoarthritis: a randomized, placebo controlled study”

Sports Medicine]; this committee will conduct a preliminary review of the existing data once 10 participants have been enrolled in each group.

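### Sections 5.3 and 13.1 name no primary outcome or time summary; if any of the five visits may be read at 5%, false positives on VAS alone reach about 10–21% per placebo contrast

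*Combined protocol and SAP*

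**What the plan says.** Section 13.1, repeated in 5.3, will "compare the post-treatment trajectory of joint pain and functionality over follow-up between a pair of treatment groups" by mixed-effects regression. It adds: "This approach facilitates group comparisons (1) at individual follow-up times, (2) life course of effects over the entire follow-up period". Repeated-measures ANCOVA and t-tests are to be considered as robustness and sensitivity checks. Section 12.1 puts the five follow-ups at 2 weeks, 6 weeks, 3 months, 6 months and 1 year, with VAS, WOMAC and KOOS at each.

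The questions come from Section 1. Under 1.1, "intra-articular corticosteroids are included as a study group to be evaluated for impact on pain relief and joint functionality in comparison to placebo". Under 1.2, Lipogems participants "will experience a decrease in pain of the affected knee and an increase in joint functionality in comparison to placebo"; a separate sentence gives the corticosteroid hypothesis, on pain or function.

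Section 13.2 treats VAS pain as a main variable of interest and sizes on it: "we assumed average change in pain score over the follow-up to be 10-15, and standard deviation to be 10-20". It continues: "To have 80% power with a 5% Type I error an approximate 2-way ANOVA model suggest sample size in the range of 18-49 per group", and then "We adopt n=22 as our minimum sample size per group based on the assumption of 15-point change in pain score over time on average", with a 20-point SD. That is the only place, with its copy in 5.3, where 5% appears.

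Section 7 is headed Study Endpoints. It gives the end of the study and a preliminary evaluation at 10 participants per group, but names no outcome. The documents state no rule for multiple comparisons.

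**The concern.** Pain and function, five visits and a whole-follow-up summary, and pairs drawn from three arms all stand on the same footing. Nothing says which of these results decides whether a treatment worked. A reader of the final report could not tell whether the comparison put forward was the intended one or the most favourable of many.

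The stated 5% protects one pre-chosen test. It does not protect a result picked from several. Once outcomes are known, naming a primary no longer repairs this. The point carries extra weight here because the outcomes are patient-reported and Lipogems participants know their assignment (3.2), so the efficacy conclusion should not also rest on a selection made after the fact.

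**Working it through.** **Inputs.** From the documents: three arms, minimum 22 and target 25 per arm (5.3), taken as equal allocation; five follow-ups (12.1); 5% Type I error, 80% power, 15-point change, SD 20 (13.2). Assumed: no true effect for the error rates, normal data, and an equal correlation ρ between any two visits of one patient. The documents give neither ρ nor the sidedness of the test.

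**1. The plan's own sample size.** For two means, n per group = 2 × [SD × (z for α + z for power) / difference]².
- One-sided 5%: 2 × [20 × (1.645 + 0.842) / 15]² = 21.98, so 22. This is the adopted figure.
- Two-sided 5%: 2 × [20 × (1.960 + 0.842) / 15]² = 27.9, so 28.
- For 10 points and SD 20, one-sided gives 49.5 (stated upper end 49); two-sided gives 62.8.

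The adopted 22 thus reproduces with this formula only as a one-sided 5% test. A three-group one-way ANOVA gives about 27 to 36 depending on the pattern of means. The stated lower end of 18 is not a corner of the stated ranges.

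**2. One pre-named VAS average.** One contrast: 5%. The two placebo contrasts share the placebo arm, so their test statistics correlate 0.5. The chance that at least one is significant is 1 − P(|Z₁| < 1.96 and |Z₂| < 1.96) = 9.07% two-sided, or 8.8% if both are one-sided at 5%. Independent tests would give 1 − 0.95² = 9.75%. This does not depend on ρ. About half of the two-sided 9% (4.5%) favours active treatment.

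**3. Any of five visits may be read, VAS only.** The chance that at least one visit reaches two-sided 5%, by simulation:

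| Assumed ρ | One placebo contrast | Both placebo contrasts |
|---|---|---|
| 0.9 | 10% | 18% |
| 0.7 | 15% | 26% |
| 0.5 | 18% | 31% |
| 0.3 | 21% | 35% |

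With correlation that decays between visits (adjacent visits 0.9 / 0.7 / 0.5), both contrasts give 21 / 30 / 35%. Function scales and the third pair of arms are left out and could only add to these figures.

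**4. Power under the possible rules.** Noncentral t, 15 points, SD 20 taken as the SD of the averaged score, n = 22 / 25:
- one-sided 5%: 79 / 83%
- two-sided 5%: 68 / 74%
- two-sided 2.5%, which is Holm's first step and applies if only one arm works: 57 / 63%

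From the apparent sizing basis to two-sided Holm the loss is 79 − 57 = 22 points at n = 22, and 83 − 63 = 20 points at n = 25.

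**The case against.** The plan is less open than it may look. Section 1 sets the placebo comparisons. Section 13.2 singles out VAS and sizes on its average over follow-up. Section 13.1 makes the mixed model the main analysis and already casts ANCOVA and t-tests as checks. All of that stands. But a sizing assumption does not bind the analysis, and 13.1 explicitly keeps every visit and function available.

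Three stronger readings are tempting, and the documents do not support them.
- *The plan breaks its own 5%, because two contrasts give 9%.* Section 1.2 states two separate hypotheses about two treatments. Answering each at 5% is a defensible convention, and nowhere is 5% promised across both arms.
- *The plan will claim efficacy from any significant visit.* The sentence on timing describes what the model makes possible and announces no such claim. The 10–35% figures show what the plan leaves open, at correlations that had to be assumed. They are not the trial's actual error rate.
- *The review at 10 per group is an unadjusted efficacy look.* Sections 7.2 and 14.3 describe a preliminary evaluation with no efficacy test or efficacy stopping rule, and the stated grounds for halting are adverse events (14.6, 22.4). No inflation can be computed from that.

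The sizing text also calls the study a pilot, which would lower the stakes. The title and Section 2 present it as an efficacy trial, and the plan does not say that confirmatory claims will be withheld.

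**Conclusion.** The omission is real and should be corrected. No primary outcome or time summary is named in 5.3, 7 or 13, and the 5% is attached only to the sizing of average VAS change. Its size depends on how the results are read. It is nil for one contrast on the VAS average (5%). It is about 10–21% per placebo contrast, and 18–35% over both, if any of the five VAS visits may be read at two-sided 5%. Those ranges assume no true effect, equal arms and ρ from 0.9 to 0.3. The 9% for two contrasts on the average counts as inflation only if the investigators intend 5% to hold jointly, so the plan needs to state which they intend.

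**What to change.** In 5.3 and 13.1, before data are seen:
- Name one primary measure. One option is the mixed-model between-arm difference in VAS averaged over the five follow-ups, with baseline VAS as a covariate. State the visit weights: with equal weights, three of the five values come from the first three months.
- Name Lipogems versus placebo and corticosteroid versus placebo as the primary contrasts.
- State the sidedness. State also whether the two contrasts are held jointly at 5% (Holm or a pre-stated order) or are separate questions at 5% each.
- Report individual visits, WOMAC, KOOS and Lipogems versus corticosteroid as secondary, with confidence intervals.

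The investigators may prefer another single time summary, or function as co-primary, provided that it and its error rule are stated beforehand. ANCOVA and t-tests can stay as they are. A sentence in 7.2 and 14.3 that the review at 10 per group makes no efficacy claim would be a useful clarification.

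The cost is text, with no added visits. Fewer results can be called significant, and a short-lived effect is diluted in an average, though still visible by visit. Power must be restated for the rule chosen: two-sided Holm gives up about 20 points against the apparent one-sided basis if only one arm works. Keeping 80% at two-sided 2.5% per contrast would need 34 per group. The restatement should also settle the SD, since 13.2 says "We estimated that the standard deviation likely to be found for our own observations will be approximately 35 on a 100 point scale, conservatively" yet sizes on 20. At SD 35, two-sided 5% power for 15 points is 28 / 32% at n = 22 / 25.

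### The 80% power statement rests on an SD of 20 that is never reconciled with the SD of about 35 the same paragraph expects

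*Combined protocol and SAP*

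**What the plan says.** Section 13.2, largely repeated in 5.3, gives the sample-size argument in four steps.

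- From the literature, it expects that "the standard deviation likely to be found for our own observations will be approximately 35 on a 100 point scale, conservatively".
- It takes a between-treatment difference in post-treatment pain of about 15 points as clinically important.
- It then assumes an average change of 10-15 and an SD of 10-20, and reports a range for each arm: "To have 80% power with a 5% Type I error an approximate 2-way ANOVA model suggest sample size in the range of 18-49".
- It settles the size in these words: "We adopt n=22 as our minimum sample size per group based on the assumption of 15-point change in pain score". The SD that goes with this is 20 points, described as applying over time.

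Section 5.3 adds an aim of 25 "or more participants in each of the three treatment arms so long as the logistics permit". It also expects that the mixed-effects model "will increase the power by utilizing the longitudinality of the data, compensating potential loss of power due to drop-outs and serial correlation".

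The planned analysis (5.3, 13.1) is a mixed-effects regression on five repeated measurements. Other methods are secondary: "We will also consider repeated measurement analysis of covariance and pairwise comparison (e.g. t-tests) to validate our analysis with respect to robustness and sensitivity". Section 12.1 collects VAS at the injection visit as baseline, then at 2 weeks, 6 weeks, 3 months, 6 months and 1 year. The variables listed in 5.3 (age, gender, diabetes status, inflammatory conditions, pre-existing joint problems, NSAID use) do not include baseline VAS, although 3.3 stratifies randomization by baseline pain severity.

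**The concern.** The paragraph moves from an expected SD of about 35 to a sizing SD of 20 with nothing in between. The two may be different quantities: 35 could describe a single score, and 20 a change or an average over follow-up. The text does not say which. It also leaves out the sidedness of the test, the within-patient correlation, and the term of the two-way ANOVA that is powered. A reader cannot get from the stated inputs to 80% without supplying at least one of these.

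This is the only justification of the sample size. Depending on what is supplied, power for a 15-point difference runs from about 30% to above 80%. If the trial ends with no clear difference between arms, nobody could say from the plan whether a clinically important difference was likely to have been detected.

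**Working it through.** **Inputs from the plan (13.2, 5.3):** difference 15 points, SD 20 or 35, Type I error 5%, power 80%, 22 or 25 per arm, five follow-up measurements.

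**Assumptions not in the plan:** the 15 points are a between-arm difference, in line with the clinical-importance sentence. Data are complete. For repeated measures, the correlation r is the same between all visits, including baseline (compound symmetry), and r is 0.5-0.7.

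**1. Reproducing the 22.** Per-arm size is n = 2(z_α + z_β)²(SD/d)², with SD/d = 20/15.

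- One-sided 5%: 2 × (1.645 + 0.842)² × (20/15)² = 21.98, so 22.
- Two-sided 5%: 2 × (1.960 + 0.842)² × (20/15)² = 27.9, so 28 (29 with the t distribution).
- Two-sided, mean of five visits, SD 20 per visit: the variance factor is (1 + 4r)/5. At r = 0.69 it is 0.752, and the effective SD is 20 × √0.752 = 17.34. Noncentral-t power at 22 per arm is then 80.0%.

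So 22 can be reached in more than one way, but each way uses an input the plan does not state.

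**2. Single measure, two-sided 5%, noncentral t with 2n − 2 degrees of freedom and noncentrality (15/SD)√(n/2).**

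| SD | 22 per arm | 25 per arm |
|---|---|---|
| 20 | 68.1% | 73.8% |
| 35 | 28.4% | 31.8% |

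**3. What would link 35 to 20.** If 35 were the single-visit SD and 20 the SD of a single-visit change from baseline, then 20² = 2 × 35² × (1 − r), so r = 1 − 400/2450 = 0.84. The plan states no such correlation.

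**4. Repeated measures if 35 is the single-visit SD.** The variance factor is (1 + 4r)/5 for the unadjusted five-visit mean. Adjusting for baseline removes r², leaving (1 + 4r)/5 − r².

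| Analysis | r | Factor | Effective SD | Power, 22 per arm | Power, 25 per arm |
|---|---|---|---|---|---|
| Five-visit mean, unadjusted | 0.5 | 0.60 | 27.1 | 43% | 48% |
| Five-visit mean, unadjusted | 0.7 | 0.76 | 30.5 | 36% | 40% |
| Five-visit mean, adjusted for baseline VAS | 0.5 | 0.35 | 20.7 | 65% | 71% |
| Five-visit mean, adjusted for baseline VAS | 0.7 | 0.27 | 18.2 | 76% | 81% |

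A simulation of 4000 trials at 25 per arm agreed with the last column: 50% and 41% unadjusted, 71% and 81% adjusted.

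**5. The same analyses if 20 is the single-visit SD.** Over r = 0.5-0.7 the unadjusted five-visit mean has 88-80% power at 22 per arm and 92-85% at 25. With baseline adjustment, power is at least 98% at 22 and 99% at 25. What the two SDs mean therefore decides the answer.

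**The case against.** The best defence is that the plan never claims 80% for a single-measure t-test. It cites an approximate two-way ANOVA, plans a mixed model on five measurements, and describes both its change and its SD as being over time. Under a two-sided five-visit reading with SD 20, the published figures can be made to cohere. A 15-point difference gives 17.8 per arm at r = 0.5 and about 22 at r = 0.69; a 10-point difference gives 48.7 at r = 0.7. On that reading, 25 per arm has more than 80% power. The text also calls the study a pilot.

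Much of this stands. A reader might infer from the 68% that 22 is a calculation error. The documents do not support that, because 22 is reproducible and the 68% belongs to a simpler test than the planned one. A reader might also infer that 18-49 is wrong. It lacks inputs, which is a different matter.

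A third tempting reading is that 5.3 counts the longitudinal gain twice, once in the 22 and again as cover for drop-out. That would follow only if the 22 already rests on averaging over visits, which the text does not say.

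The defence does not supply the missing link. The coherent reading needs a correlation the plan never gives, uses only the top of the assumed SD range of 10-20, and leaves the expected SD of 35 unexplained. Calling the study a pilot lowers the stakes but does not support the 80%.

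**Conclusion.** This is an unsupported power statement, and it should be fixed. If 35 is the single-visit SD, the unadjusted five-visit comparison at 25 per arm has 48-40% power for 15 points. Only the baseline-adjusted version approaches the target, at 71-81%, and it passes 80% only near the top of the assumed correlation range. Other analyses reach 80% at SD 35 and 25 per arm only with higher correlations: about 0.77 or more for five-visit mean change from baseline, and about 0.85 or more for a single-visit ANCOVA.

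These figures rest on a two-sided 5% test, complete data, compound symmetry from baseline to one year, and r of 0.5-0.7, which is an assumption. It would go too far to conclude that SD 20 is wrong or that the trial is underpowered. The documents leave open that 20 and 35 describe different quantities, and with 20 as the single-visit SD the planned size is adequate. They do not show which case applies.

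**What to change.** Two changes, with no change in enrolment.

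1. In 5.3 and 13.2, state whether 20 and 35 are single-visit, change or averaged SDs. Declare the test two-sided at 5%, and name the mixed-model comparison that is powered. Restate power at 22 and 25 per arm under both SDs, with the within-patient correlation given as a range. For a five-visit mean, if each SD is taken as single-visit, the text could read:

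> Two-sided 5%, 15-point difference, 22 / 25 per arm, assumed correlation 0.5-0.7. SD 20: 88-80% / 92-85% unadjusted, at least 98% / 99% adjusted for baseline VAS. SD 35: 43-36% / 48-40% unadjusted, 65-76% / 71-81% adjusted.

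   If 20 is already the SD of an averaged change, the two-sided figure to print for it is 68% / 74%, with no further gain from averaging.

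2. Add baseline VAS as a covariate in the primary mixed model. It is already collected at the injection visit. At SD 35 and 25 per arm it raises power from 48-40% to 71-81% under the same assumptions.

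The cost is wording in two sections and one model term, with no added visits or patients. The downside is that the stated power may become less favourable than 80%.
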